Patients with SCD will be recruited from the sickle cell clinic at the University of Chicago Medical Center. 172 patients will be needed to adequately power the study. Based on prior experience 15% of patients will have inadequate perfusion MRI data quality; therefore, approximately 200 patients will be enrolled into the study. As most of these patients are already enrolled in TRIDOM (Translational Research Initiative in the Department of Medicine), plasma screens for the markers listed earlier will be conducted using the blood already available from this initiative and hence new blood draws will not be needed. For the patients who are not enrolled in TRIDOM yet, we will inform of them of their opportunity to participate in the program (but not require them to participate) while also recruiting them for this study. In addition, 20 control subjects (age, race, and sex distributions similar to those of the SCD patients) will be used to determine baseline or normal values for myocardial blood flow, LV size and function, RV size and function, and myocardial iron content (i.e. T2* values). These normal ranges will be specific for the techniques and equipment used at The University of Chicago Medical Center. Healthy control subjects will not be eligible if they have a history of coronary artery disease or renal insufficiency based on direct

questioning. For all subjects who do not have a blood sample available from TRIDOM, we will collect a blood sample from them as part of this study (about 20 ml or 4 teaspoons).

a) Inclusion criteria

- Patients must be 18+.
- Patients who were diagnosed with SCD confirmed by high-pressure liquid chromatography or hemoglobin electrophoresis will be eligible for the study.
- Only outpatients in stable condition will be included.
- Patients receiving transfusions will not be excluded.

b) *Exclusion criteria*

- Patients with a history of vaso-occlusive crises or an episode of acute chest syndrome within the previous four weeks will be evaluated at a later time.
- Patients with high degree heart block; active, hemodynamically significant, ventricular arrhythmias; unstable coronary syndromes; history of myocardial infarction within 1 month of the study.
- Contraindications to gadolinium-enhanced magnetic resonance examination:
 - severe claustrophobia,
 - Pacemaker, defibrillators, cerebral aneurysm clips, or neurostimulator.
 - GFR<30 mL/min/m²
- Pregnancy
- Patients with sinus node dysfunction

II. *Data collection*

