Whole genomic SNP survey- This proposal will utilize the new Affymetrix® Genome-Wide Human SNP Array 6.0 with 1.8 million genetic markers (including more than 906,600 single nucleotide polymorphisms (SNPs) and 946,000 probes for the detection of copy number variation). Given the large numbers of probes, the SNP Array 6.0 will enable the design of this association study to take advantage of larger sample sizes in the proposal, thereby significantly increasing the overall genetic power. Briefly, total genomic DNA (500 ng), obtained from the TRIDOM initiative, will be utilized for the amplification and technical protocol as recommended by the Affymetrix manufacturer. PCR conditions have already been optimized to preferentially amplify fragments. Affymetrix Genome-Wide Human SNP Array 6.0 contains validated and qualified reagents for the most critical steps in the assay. This includes the PCR primer and adaptors, reagents to fragment and label the PCR products and several control reagents. Details of this kit and protocol are all available from the Affymetrix website (http://www.affymetrix.com/products/arrays/specific/genome_wide_snp6/genome_wide_snp_6.affx). The measurements and analyses for all of the SNP, gene, and microRNA studies will be performed at the Functional Genomics facility here at the University of Chicago Medical Center (details of the protocols for DNA, RNA, and microRNA isolation and measurement protocols as well as quality control are described at <http://fgf.uchicago.edu/>).

Gene and microRNA Expression Profiling- This proposal will utilize the GeneChip® Human Gene 1.0 ST Array by Affymetrix (details at the website) for gene expression profiling, covering 28,869 genes represented on the array by approximately 26 probes spread across the full length of an individual gene. The Human Gene 1.0 ST Array has greater than 99 percent coverage of sequences present in the RefSeq database. To determine microRNA differences, this proposal plans to use the mercury LNA microRNA array offered by Exiqon. The array provides access for examination of over 1300 human microRNAs with as little as 30ng total RNA (obtained from the TRIDOM initiative). Details of this technology are also provided at <http://www.exiqon.com>.

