Soluble protein levels of select biomarkers will be assessed via commercially available enzyme-linked immunoassay kits for VCAM-1, ICAM-1, E-selectin (Invitrogen Corporation), NOx (Cayman Chemical), P-selectin, erythropoietin and VEGF (R&D Systems) according to manufacturer's instructions (blood obtained from the TRIDOM initiative).

e) Statistical Consideration

The study will be powered to detect a 10% difference in myocardial blood flow in sickle cell patients with and without pulmonary hypertension. Because myocardial blood flow has the highest variability of all the measurements to be collected in this study, the study will be adequately powered to detect differences in all the other measurements that will be made. Based on my previously published work involving MRI measurements of myocardial blood flow, in order to detect an approximately 10% difference in perfusion reserve between groups, 54 subjects will be needed in each group (alpha 5%, beta 50%). Approximately 40% of sickle cell patients have pulmonary hypertension. In order to recruit enough sickle cell patients with pulmonary hypertension to adequately power the study, approximately 150 subjects in total with sickle cell disease will need to be recruited. Differences in the various left and right ventricular function and size measurements derived from the sickle cell disease population will be compared to age and gender matched controls using t-tests. The sickle cell disease population will be divided into two groups: those with pulmonary hypertension (as determined by Doppler echocardiography) and those without

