pulmonary hypertension. Differences in left ventricular and right ventricular systolic function, diastolic function, myocardial perfusion reserve, myocardial scar burden, and myocardial iron content that exist between the two groups will be determined by t-tests. Linear regression analysis will be used to compare the severity of pulmonary hypertension with each of the above mentioned continuous variables. The sickle cell disease population will also be divided into another 2 groups: those with diastolic dysfunction and those without diastolic dysfunction. Once again, the above listed parameters will be compared using t-tests. Patients with diastolic dysfunction will also be classified according to a well established grade of severity, and the relationship between the various continuous variables and the severity of diastolic dysfunction will be investigated through analysis of variance (ANOVA). A p-value <0.05 will be considered statistically significant.

f) *Data Safety*

Included patients will be issued a unique identifying number that will be linked to the collected data. No personal identifiers such as name, medical record number or address will be stored with this data. A separate list linking the patients' unique identifying number and their medical record number will be stored on a different computer. All electronic data will be protected using secure, password protected computer files. Physical charts will be kept in a cabinet under lock and key. This system will ensure that patient information is protected and accessible only to the principal investigators and co-investigators. Data will only be used for the research study.

4. Special precautions to be taken by the researchers (*including dose modifications and whether subjects will be asked to take a pregnancy test before and, as applicable, during the study*).

Any female patient that is enrolled in the study will be tested for pregnancy using a urine test.

5. Exact location where research is to be conducted:

The following locations will be utilized for the proposed study:

- University of Chicago Medical Center Outpatient Clinics
- [name] Sickle Cell Clinic
- University of Chicago Medical Center Echocardiography laboratory
- University of Chicago Medical Center MRI facility
- Outpatient lab collection

6. Duration of protocol:

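### The SNP survey is credited with increased genetic power, but a sample of about 200 sized on imaging gives 80% genome-wide power only for large single-SNP effects

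*Combined protocol and SAP*

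**What the plan says.** Section 3 (Methods), II, Whole genomic SNP survey, plans an array of 1.8 million markers, "including more than 906,600 single nucleotide polymorphisms (SNPs) and 946,000 probes for the detection of copy number variation". It then says that this number of probes enables the association study "to take advantage of larger sample sizes in the proposal, thereby significantly increasing the overall genetic power". It gives no effect size, allele frequency, threshold or power figure.

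Sample size comes from elsewhere. Section 3, I (Selection of patients) says "172 patients will be needed to adequately power the study", adds that "Based on prior experience 15% of patients will have inadequate perfusion MRI data quality", and concludes that "approximately 200 patients will be enrolled into the study". Section 3, II, e (Statistical Consideration) bases the sizing on perfusion reserve, with 54 subjects per group at alpha 5% and beta 50%, and says "Approximately 40% of sickle cell patients have pulmonary hypertension". It reasons that myocardial blood flow is the most variable measurement, so the study is adequately powered for all the others.

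The planned analyses are t-tests, linear regression and ANOVA, with one criterion: "A p-value <0.05 will be considered statistically significant". No SNP model and no multiplicity control are described. Section 2, Aim 2, describes the polymorphism work as targeted at selected candidate genes and linked to a quantitative PH phenotype, which is a narrower scope than a whole-genome survey.

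**The concern.** The power claim does not follow from its premise. A denser array covers more of the genome, but the number of patients stays at about 200, and each added SNP makes the per-test threshold stricter if the overall error rate is controlled.

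The general statement in the Statistical Consideration section does not close the gap. It compares the variability of measurements that are each tested once at 5%. It takes no account of hundreds of thousands of tests.

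Aim 2 is one of only two aims, so this affects what the study can conclude. A reader who accepts the two statements could take a null survey as evidence against a genetic contribution to PH, or could give a nominally significant SNP the credit due to an adequately powered search.

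**Working it through.** **The plan's own figures.** There is no genetic power figure to reproduce. The enrolment figure does reproduce: 172 / (1 − 0.15) = 202.4, so 203, which agrees with about 200.

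**Inputs from the documents.** N = 200 enrolled (172 before the allowance for unusable perfusion MRI); 906,600 SNPs; PH share 40%, so 0.40 × 200 = 80 with PH and 120 without.

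**Assumptions not in the documents.** Two-sided Bonferroni control; an additive (allelic) model; allele frequency in the non-PH group of 0.1 or 0.3; 100 SNPs for the candidate-gene case.

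**Thresholds.**
- Genome-wide: 0.05 / 906,600 = 5.5e-8, critical z = 5.434.
- Candidate genes: 0.05 / 100 = 0.0005, critical z = 3.481.

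**Quantitative PH phenotype.** A 1-df test has non-centrality N·R²/(1 − R²), where R² is the share of variance explained by one SNP. For 80% power the non-centrality must be (critical z + 0.842)², and R² = non-centrality / (N + non-centrality).
- Genome-wide: (5.434 + 0.842)² = 39.4. At N = 200, R² = 39.4 / 239.4 = 16.5%. At N = 172, R² = 39.4 / 211.4 = 18.6%.
- 100 candidate SNPs, N = 200: (3.481 + 0.842)² = 18.7, so R² = 18.7 / 218.7 = 8.5%.
- Power at R² = 5%, N = 200: non-centrality = 200 × 0.05 / 0.95 = 10.53, square root 3.244. Genome-wide: Φ(3.244 − 5.434) = Φ(−2.19) = 1.4%. With 100 SNPs: Φ(3.244 − 3.481) = 41%.

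**PH against no PH (160 against 240 alleles).** For odds ratio OR and non-PH frequency p₀, the PH frequency is p₁ = OR·p₀ / (1 − p₀ + OR·p₀). Power is approximately Φ(|p₁ − p₀| / SE − critical z), with SE² = p₁(1 − p₁)/160 + p₀(1 − p₀)/240.
- OR 2, p₀ = 0.3: p₁ = 0.6 / 1.3 = 0.4615, difference 0.1615, SE = 0.0493, ratio 3.28. Genome-wide power = Φ(3.28 − 5.434) = 1.6%. With 100 SNPs: Φ(3.28 − 3.481) = 42%.

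Solving the same expression for 80% power at the genome-wide threshold gives the table below. The pooled column uses the pooled variance in the critical value.

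| Allele frequency | OR, unpooled variance | OR, pooled variance |
|---|---|---|
| 0.3 | 3.58 | 3.73 |
| 0.1 | 5.25 | 5.04 |

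**The only threshold in the plan.** If p < 0.05 were applied to each SNP, power at OR 2 and frequency 0.3 would be about 91%. However, 906,600 × 0.05 = 45,330 SNPs would be expected to pass if none were associated.

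**The case against.** *The documents limit the SNP work to candidate genes.* Aim 2 does say so, and this carries weight. With an assumed 100 SNPs, power is 41% at R² = 5% and 42% at OR 2, which is modest rather than negligible. But the power claim is made in the whole-genome section, and 80% power would still need R² of about 8.5%. The two descriptions of scope need reconciling whichever is meant.

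*The threshold is imported.* This is correct: the plan names no genome-wide alpha and no correction. The figures are therefore conditional on Bonferroni control. The alternative on the page, p < 0.05 per SNP, gains power only by accepting tens of thousands of expected false positives.

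*The survey has almost no power for any realistic effect.* A reader might infer this stronger point, but the documents do not support it. They give no effect size or allele frequency for any SNP, so they do not show what is realistic. Power is also not negligible for large effects: at frequency 0.3 it is 42% at OR 3 and 88% at OR 4 (pooled variance), and it is 69% at R² = 15%.

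*The sentence is loose and relative.* It credits power to larger sample sizes, gives no number, and does not itself call the survey adequately powered. That is fair. However, it presents probe count as what enables the gain, and the Statistical Consideration section supplies the adequacy statement without excluding the SNP work.

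*Nothing says a null result will be over-read.* This also stands: the misreading is a risk that the wording leaves open, not a stated intention. The N = 172 figure is only a sensitivity case. The 15% loss concerns perfusion MRI, while PH is defined by Doppler echocardiography, so those patients need not be lost to the genetic analysis.

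**Conclusion.** The concern holds in conditional form. The plan claims increased genetic power and general adequacy, and neither is shown or supported for the SNP survey.

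Under Bonferroni control over 906,600 SNPs, about 200 patients reach 80% power only for a SNP explaining about 16.5% of the variance in PH severity. For PH against no PH, the allelic odds ratio must be about 3.6 to 3.7 at frequency 0.3, or 5.0 to 5.2 at frequency 0.1. A candidate-gene analysis lowers these requirements without making the survey well powered for moderate effects.

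The conclusion rests on the assumed threshold, the additive model and the 40% PH share. The choice of variance formula moves the odds ratios slightly and does not change the conclusion. The point concerns the SNP survey alone and does not bear on the imaging comparisons.

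**What to change.** 1. In the Whole genomic SNP survey section, delete the claim of increased genetic power.
2. In Statistical Consideration, exclude the SNP survey from the statement that all other measurements are adequately powered.
3. State the detectable effect together with its threshold. For example: with about 200 genotyped patients and a two-sided Bonferroni threshold of 5.5e-8 (0.05/906,600), the survey has 80% power for a single SNP explaining about 16.5% or more of the variance in PH severity.
4. Reconcile the candidate-gene scope in Aim 2 with the whole-genome survey in Methods. If candidate genes are meant, give their number and recompute the threshold and detectable effect from it.
5. State that SNP results are hypothesis-generating and that a null result does not exclude a genetic contribution to PH.

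The cost is wording only, with no change to recruitment, assays or patient procedures. The stated claim becomes less favourable.

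### Highest variability in blood flow does not establish adequate power for all other measurements; at most it covers continuous measures, for the same 10% difference, PH versus no PH

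*Combined protocol and SAP*

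**What the plan says.** All references are to the combined protocol and SAP, section 3 (Methods).

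Part II e), Statistical Consideration, powers one contrast: SCD patients with and without PH, for a 10% difference in myocardial blood flow. It then gives a reason: "Because myocardial blood flow has the highest variability of all the measurements to be collected in this study". From this premise alone it concludes that "the study will be adequately powered to detect differences in all the other measurements that will be made". The calculation itself is stated for a difference of about 10% in perfusion reserve: "54 subjects will be needed in each group (alpha 5%, beta 50" per cent). With about 40% of patients expected to have PH, "approximately 150 subjects in total with sickle cell disease will need to be recruited".

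The same part goes on to plan other comparisons:
- Left and right ventricular measures in SCD patients "will be compared to age and gender matched controls using t-tests".
- T-tests between patients with and without diastolic dysfunction, and an ANOVA by grade. No group sizes are given.
- A t-test of scar burden between the PH groups. Part II b) records late enhancement as present or absent in each of 17 segments.

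Part I, Selection of patients, says that "20 control subjects (age, race, and sex distributions similar to those of the SCD patients) will be used to determine baseline or normal values". It also gives different totals: "172 patients will be needed to adequately power the study", and because "15% of patients will have inadequate perfusion MRI data quality", about 200 are to be enrolled.

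**The concern.** Power depends on the difference sought relative to the SD and on the group sizes. The sentence speaks only to variability. The documents give no SD for any measurement and no target difference for anything beyond blood flow or perfusion reserve. They also give no diastolic-dysfunction group sizes. The conclusion is therefore wider than its premise.

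This affects how null results are read. A non-significant result in a comparison described in advance as adequately powered tends to be taken as evidence of no difference. For the control, diastolic-dysfunction and scar comparisons, the plan offers no basis for that reading.

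**Working it through.** **Inputs from the plan.** 54 per group; alpha 5%; beta 50%; a 10% difference; PH share 40%; totals of 150, 172 and about 200; 15% loss of perfusion data; 20 controls.

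**Assumptions.** Two-sided test (sidedness is not stated); normal data; equal SDs in the groups compared unless noted. Beta of 20% and 5% are shown beside the printed 50%, in case the printed value is an error.

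**Formula.** With d = difference/SD, the noncentrality is d × √[n1·n2/(n1+n2)] on n1+n2−2 degrees of freedom. Power is the chance that a noncentral t exceeds the 5% two-sided critical value.

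**1. The plan's own figure.** The 54 per group cannot be reproduced, because no SD is given. Solving backwards with n1·n2/(n1+n2) = 54×54/108 = 27:

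| Beta | Implied d | SD as % of mean for a 10% difference (10/d) |
|---|---|---|
| 50% | 0.381 | 26.2 |
| 20% | 0.544 | 18.4 |
| 5% | 0.700 | 14.3 |

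As printed, the reference power is 50%.

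**2. What the premise does cover.** For a 10% difference, d = 10%/(SD as % of mean). If another continuous measure has a relative SD no larger than that of blood flow, its d is no smaller, so its power in the same contrast is no lower. The group sizes are 40%/60% of 150 (60/90), of 200 × 0.85 = 170 (68/102), and of 200 (80/120). At d = 0.381, power is 62%, 68% and 75%. The differences detectable at 80% power are 0.47, 0.44 and 0.41 SD.

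**3. SCD versus 20 controls.** n1·n2/(n1+n2) is 20×150/170 = 17.6 and 20×200/220 = 18.2. It stays below 20 for any number of patients, against 27 for 54/54.

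| Beta | Power at 54/54 | Power, 20 vs 150 to 200 |
|---|---|---|
| 50% | 50% | 36–37% |
| 20% | 80% | 62–64% |
| 5% | 95% | 83–84% |

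The difference detectable at 80% power is 0.67 SD (150) to 0.66 SD (200). The 95% confidence interval half-width, t × √(1/20 + 1/N), is 0.47 to 0.46 SD.

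Two conditions would each bring this comparison level with 54/54:
- *Smaller relative SD of the measure.* The ratio to that of blood flow must be at most about √(17.6/27) = 0.81 for 150 patients and √(18.2/27) = 0.82 for 200. Exact values, allowing for degrees of freedom, are 0.811 and 0.824, the same at each beta.
- *Less variable controls.* With r = control SD/patient SD, set r²/20 + 1/N = 2/54. Then r = √[20(2/54 − 1/N)], which is 0.78 at N = 150 and 0.80 at N = 200.

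Being less variable than blood flow guarantees only a ratio below 1. The documents do not show whether either condition holds.

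**4. Diastolic dysfunction.** A share f in the smaller group matches 54/54 when N·f(1−f) = 27. That gives f = 23.5% of 150 or 16.1% of 200. The plan states no share.

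**5. Scar.** Segment readings can be summed into a burden score and t-tested, or treated as any versus none. The first needs a relative SD and the second an event rate. Neither is given, so the premise cannot be applied.

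**The case against.** The strongest reply is that the sentence follows one that names only PH versus no PH, so it may mean other measurements within that contrast. The valid core in step 2 then stands. However, the sentence carries no such limit, and the same section goes on to plan the control and diastolic-dysfunction t-tests. Even within the PH contrast it says nothing about differences smaller than 10%, or about scar.

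Several other replies do hold, and they limit the point:
- **Equal SDs.** Every control figure in step 3 assumes equal SDs, and so does any ranking of the control t-tests as the least precise. Controls about 20–22% less variable than patients would remove the gap.
- **Beta.** If 5% was intended, the control comparison exceeds 80% power at the implied difference, so it is not inadequate under every reading.
- **Borrowed difference.** The plan sets no 10% target for patients versus controls, and it describes the controls as a source of normal values. Applying the PH-contrast difference there is an illustration only.
- **Scar.** Segment-level coding does not by itself rule out a t-test of burden.

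A reader might infer that the control, diastolic-dysfunction and scar comparisons are underpowered. The documents do not support that: without SDs, target differences and group sizes, neither adequate nor inadequate power can be shown.

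**Conclusion.** The assurance is wrong as written because it is unsupported beyond a limited set: continuous measures with relative SD no larger than that of blood flow, a 10% difference, and PH versus no PH. Even that rests on an asserted ranking of variability and, at the printed beta, on 50% power at 54/54.

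For equal standardized difference and equal SDs, the control comparison falls about 11 to 18 percentage points short of 54/54, depending on beta (95 − 84 = 11; 80 − 62 = 18). This is a gap relative to the reference design under those assumptions, not proof of low power for any particular ventricular measure. For diastolic dysfunction and scar the size of any shortfall is unknown. No figure in the plan is shown to be miscalculated. The fault is an inference drawn too widely.

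**What to change.** Replace the sentence with a qualified one, for example: *If blood flow has the largest SD relative to its mean, other continuous measures will have at least the same power for the same 10% relative difference between SCD patients with and without pulmonary hypertension.*

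Then:
- Confirm which total applies (150, or 172 with about 200 enrolled), and state the differences detectable at 80% power for it, using the matching values from steps 2 and 3. The 68/102 figure is for perfusion measures and the 80/120 figure for measures without the 15% loss. Label the control figure as assuming equal SDs.
- Report the planned control t-tests with 95% confidence intervals.
- Say that power for the diastolic-dysfunction and scar comparisons is not established.

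The cost is wording, a decision on the total, and confidence intervals beside tests already planned. No patients, controls or tests change. The downside for the sponsor is that the stated power becomes narrower and less favourable.

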b) CMR will be performed on all patients. Patients will be asked to not eat or drink for 6 hours prior to the CMR study. Additionally, beta-blockers, rate-lowering calcium channel blockers, and nitrates will be held on the morning of the study. Upon arrival to the MRI unit, an 18-gauge IV will be placed in the upper extremity. EKG leads will be attached to the patient's chest wall and a flexible surface coil will be placed over the thorax. The blood pressure and heart rate will be monitored throughout the study. Steady state free precession imaging will be performed to quantify left and right ventricular size and function and T2* images will be acquired to determine whether myocardial iron overload is present. In order to assess microcirculatory function, first-pass perfusion CMR using Gd-DTPA will be performed under resting and hyperemic conditions. The subject will receive a 0.4mg bolus of intravenous regadenoson to induce hyperemia. Immediately afterwards, 0.01 mmol/kg of Gd-DTPA will be infused intravenously at a rate of

0.5 ml/ sec followed by a 0.1mmol/ kg infusion of Gd-DTPA at a rate of 5ml/sec. Images will be acquired as the Gd-DTPA transits the left ventricle using a hybrid GRE-EPI pulse sequence [25]. The same perfusion protocol will be repeated under resting conditions. Using time intensity curves extracted from the acquired images, the absolute resting myocardial blood flow, hyperemic myocardial blood flow, and perfusion reserve will be calculated for each of the 16 American Heart Association myocardial segments using a Fermi function deconvolution [26]. A perfusion reserve <1.85 will be considered abnormal. After the perfusion imaging is completed, late gadolinium enhancement using an inversion recovery technique will be used to detect the presence of myocardial scar. The presence or absence of late gadolinium enhancement will be determined for each of the 17 American Heart Association myocardial segments. The presence of any late gadolinium enhancement will be considered abnormal. Clinically relevant results from the cardiac MRI study will be dictated and reported to the patient's physician.

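### The only power calculation prints a beta of 50%, which conflicts with three statements that the study is adequately powered, and the documents do not show which is wrong

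*Combined protocol and SAP*

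**What the plan says.** Section 3, Methods, II. Data collection, e) Statistical Consideration holds the only power calculation in the protocol: "54 subjects will be needed in each group (alpha 5%, beta 50" per cent). The variability behind it is credited to the investigator's earlier published work, with no number. The analysis threshold is p<0.05, with no statement of one or two sides.

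The protocol claims adequate power three times:

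- Section 3, I. Selection of patients: "172 patients will be needed to adequately power the study".
- Statistical Consideration, on the total: "to adequately power the study, approximately 150 subjects in total with sickle cell disease will need to be recruited".
- Statistical Consideration, on everything else measured: "the study will be adequately powered to detect differences in all the other measurements that will be made".

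The target variable is given in two ways. The section opens with "The study will be powered to detect a 10% difference in myocardial blood flow in sickle cell patients with and without pulmonary hypertension". The sentence that yields 54 instead reads "in order to detect an approximately 10% difference in perfusion reserve between groups". Under Data collection, item b), these are distinct outputs: "the absolute resting myocardial blood flow, hyperemic myocardial blood flow, and perfusion reserve will be calculated" for each segment.

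**The concern.** Beta is the probability of missing a true difference of the target size, so 50% means that the study was sized to miss it half the time. No usual meaning of adequate power covers that. Either the printed beta is wrong or the three adequacy statements are.

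The choice matters because the whole sample size rests on this one calculation, and the protocol extends its adequacy to every other measurement on the ground that blood flow is the most variable. A null comparison of patients with and without PH would be fairly informative at 93% power and much less so at 68%. A reader of the plan cannot tell which applies.

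**Working it through.** **Inputs from the documents**

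- Alpha 5%, printed beta 50%, 54 per group, target difference about 10% (Statistical Consideration).
- Two-sample t-tests, PH versus no PH (same section).
- PH in about 40% of patients (same section); the background section gives 30 to 40%.
- Enrolment of about 200 (Selection of patients), where also "Based on prior experience 15% of patients will have inadequate perfusion MRI data quality".
- SD, CV, reference mean, sidedness: not given.

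**Step 1. Can 54 be reproduced?** No. The normal-approximation formula is n per group = 2 × (z_alpha + z_power)² × (CV / 10%)², and the CV is missing. The formula can only be inverted: CV = 10% × √(54/2) / (z_alpha + z_power). For two-sided 5% and 50% power this is 10% × 5.196 / (1.960 + 0) = 26.5%. For 80% power it is 10% × 5.196 / (1.960 + 0.842) = 18.5%. So 54 fits any power, depending on the CV.

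**Step 2. Exact version.** With the noncentral t distribution and equal SDs, solve for the standardised difference d that gives the stated power at 54 versus 54; then CV = 10% / d.

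**Step 3. Expected evaluable split.** 200 × 0.85 = 170; 170 × 0.40 = 68 with PH; 170 − 68 = 102 without.

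**Step 4. Power for a 10% difference at 68 versus 102, by intended beta**

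| Intended beta | d, two-sided | Implied CV | Power | d, one-sided | Implied CV | Power |
|---|---|---|---|---|---|---|
| 50% (as printed) | 0.381 | 26.3% | 68% | 0.319 | 31.4% | 65% |
| 20% | 0.544 | 18.4% | 93% | 0.482 | 20.8% | 92% |
| 10% | 0.630 | 15.9% | 98% | 0.567 | 17.6% | 98% |
| 5% | 0.700 | 14.3% | 99% | 0.637 | 15.7% | 99% |

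**Step 5. Difference detectable with 80% power if 50% is literal.** At 68 versus 102, two-sided, 80% power needs d = 0.441, and 0.441 × 26.3% = 11.6%. One-sided, the figure is 12.3%.

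**Step 6. Other splits that the documents allow (two-sided)**

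| Split | Power if beta 50% | Power if beta 20% |
|---|---|---|
| 150 evaluable, 40% PH: 60 vs 90 | 62% | 90% |
| 170 evaluable, 30% PH: 51 vs 119 | 62% | 90% |
| 170 evaluable, 40% PH: 68 vs 102 | 68% | 93% |

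On the literal reading, no split in this table reaches 80%.

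**The case against.** The strongest reply is that no arithmetic error is shown. The 50% is probably a misprint, 54 may be correct, and the 50% belongs to 54 versus 54, whereas the totals called adequate are larger. The protocol also never defines adequate, so the conflict is with ordinary usage and not with a stated target. All of this is fair, and it is why the point stops short of calling the study underpowered. It does not remove the conflict. The larger totals still give only 62 to 68% on the literal reading, and a misprint could stand for 20%, 10% or 5%, each with a different CV.

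A second reply is that the powered variable can largely be inferred: the sentence with 54 names perfusion reserve, and so does the list of planned t-tests, which does not name resting or hyperemic flow. That is a good reason to expect perfusion reserve to be the answer. The opening sentence still says blood flow, so this is a secondary correction, but it decides which CV has to be retrieved.

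A third reply is that the 68 versus 102 split is favourable. That is also correct: with 30% PH the PH group would be 51, below the 54 that the protocol requires. The gap between the readings is then 62% against 90%, in place of 68% against 93%.

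**Conclusion.** The concern holds. The plan is wrong as written: a stated beta of 50% and three claims of adequate power cannot all stand, and nothing else in the documents decides between them. Taking the protocol's own 40% PH and 15% loss from 200, a two-sided 5% test and equal SDs, power for a 10% difference is about 68% if the printed beta is literal, and 93% or more if it stands for 20% or less. Every one of these figures is back-solved from 54 per group, so each is conditional on which beta was meant. None is an estimate of the study's true power, which depends on a CV that the documents do not report. It must be fixed, because it is the only justification given for the sample size.

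**What to change.** In Statistical Consideration, state:

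- the intended beta;
- the SD or CV, with its source in the earlier work;
- whether the test is one- or two-sided;
- one powered variable: perfusion reserve, or myocardial blood flow with resting or hyperemic specified.

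Recompute the number per group from those inputs, and report power at the expected evaluable split of about 68 versus 102.

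If beta is a misprint for 20%, 10% or 5%, correct that number; 54 then stands once the documented CV reproduces it. If 50% is confirmed, withdraw the adequacy wording in Selection of patients and in Statistical Consideration, and report the power that the documented CV gives. That would be about 68% for a 10% difference, or 80% for about 11.6%, only if the CV proves to be near 26% and the test two-sided.

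The cost is wording plus retrieval of one variability figure; the stated power may become less favourable. The correction itself needs no added enrolment and no change of test. More patients would come into question only if 50% is confirmed and the sponsor still wants 80% power for a 10% difference. With the implied CV, a two-sided test and a 40:60 split, that would take about 230 evaluable against the 170 expected.
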